PSRAE Possible Suicidality Related Adverse Event PUVA Psoralen and Ultraviolet A QD Once Daily QTc QT Duration Corrected for Heart Rate QTcF QT Duration Corrected for Heart Rate by Fridericia's Formula QTL Quality Tolerance Limit RA Rheumatoid Arthritis RAMOS NG Randomization and Medication Ordering System New Generation RBC Red Blood Cell RIP1 Receptor-Interacting Protein 1 RIPK1 Receptor-interacting serine/threonine-protein kinase 1 RNA Ribonucleic acid	PLSS	Psoriatic Lesion Severity Sum
PUVA Psoralen and Ultraviolet A QD Once Daily QTc QT Duration Corrected for Heart Rate QTcF QT Duration Corrected for Heart Rate by Fridericia's Formula QTL Quality Tolerance Limit RA Rheumatoid Arthritis RAMOS NG Randomization and Medication Ordering System New Generation RBC Red Blood Cell RIP1 Receptor-Interacting Protein 1 RIPK1 Receptor-interacting serine/threonine-protein kinase 1 RNA Ribonucleic acid	PsO	Psoriasis
QD Once Daily QTc QT Duration Corrected for Heart Rate QTcF QT Duration Corrected for Heart Rate by Fridericia's Formula QTL Quality Tolerance Limit RA Rheumatoid Arthritis RAMOS NG Randomization and Medication Ordering System New Generation RBC Red Blood Cell RIP1 Receptor-Interacting Protein 1 RIPK1 Receptor-interacting serine/threonine-protein kinase 1 RNA Ribonucleic acid	PSRAE	Possible Suicidality Related Adverse Event
QTc QT Duration Corrected for Heart Rate QTcF QT Duration Corrected for Heart Rate by Fridericia's Formula QTL Quality Tolerance Limit RA Rheumatoid Arthritis RAMOS NG Randomization and Medication Ordering System New Generation RBC Red Blood Cell RIP1 Receptor-Interacting Protein 1 RIPK1 Receptor-interacting serine/threonine-protein kinase 1 RNA Ribonucleic acid	PUVA	Psoralen and Ultraviolet A
QTcF QT Duration Corrected for Heart Rate by Fridericia's Formula QTL Quality Tolerance Limit RA Rheumatoid Arthritis RAMOS NG Randomization and Medication Ordering System New Generation RBC Red Blood Cell RIP1 Receptor-Interacting Protein 1 RIPK1 Receptor-interacting serine/threonine-protein kinase 1 RNA Ribonucleic acid	QD	Once Daily
QTL Quality Tolerance Limit RA Rheumatoid Arthritis RAMOS NG Randomization and Medication Ordering System New Generation RBC Red Blood Cell RIP1 Receptor-Interacting Protein 1 RIPK1 Receptor-interacting serine/threonine-protein kinase 1 RNA Ribonucleic acid	QTc	QT Duration Corrected for Heart Rate
QTL Quality Tolerance Limit RA Rheumatoid Arthritis RAMOS NG Randomization and Medication Ordering System New Generation RBC Red Blood Cell RIP1 Receptor-Interacting Protein 1 RIPK1 Receptor-interacting serine/threonine-protein kinase 1 RNA Ribonucleic acid	QTcF	QT Duration Corrected for Heart Rate by Fridericia's Formula
RA Rheumatoid Arthritis RAMOS NG Randomization and Medication Ordering System New Generation RBC Red Blood Cell RIP1 Receptor-Interacting Protein 1 RIPK1 Receptor-interacting serine/threonine-protein kinase 1 RNA Ribonucleic acid	QTL	-
RAMOS NG Randomization and Medication Ordering System New Generation RBC Red Blood Cell RIP1 Receptor-Interacting Protein 1 RIPK1 Receptor-interacting serine/threonine-protein kinase 1 RNA Ribonucleic acid		
RBC Red Blood Cell RIP1 Receptor-Interacting Protein 1 RIPK1 Receptor-interacting serine/threonine-protein kinase 1 RNA Ribonucleic acid	RAMOS NG	
RIP1 Receptor-Interacting Protein 1 RIPK1 Receptor-interacting serine/threonine-protein kinase 1 RNA Ribonucleic acid		
RIPK1 Receptor-interacting serine/threonine-protein kinase 1 RNA Ribonucleic acid		
RNA Ribonucleic acid		
	RNA-seq	Ribonucleic Acid sequencing

RNA PCR	Ribonucleic Acid Polymerase Chain Reaction
RT-qPCR	Reverse Transcriptase Quantitative Polymerase Chain Reaction
SAE	Serious Adverse Event
SAP	Statistical Analysis Plan
SARS-CoV-2	Severe Acute Respiratory Syndrome-Related Coronavirus 2
SIB	Suicidal Ideation Behavior
sIGA	Static Investigator's Global Assessment of Disease Activity
SC	Subcutanous
SDR	Source Document Review
SDV	Source Data Verification
SGOT	Serum Glutamic-Oxaloacetic Transaminase
SGPT	Serum Glutamic-Pyruvic Transaminase
SoA	Schedule of Activities
SPF	Sun Protection Factor
SRM	Study Reference Manual
SRT	Safety Review Team
SUSAR	Suspected unexpected serious adverse reactions
TB	Tuberculosis
TEAR1	Target Engagement Assay RIP1
TH1	T Helper Type 1
TH17	T Helper Type 17
TH22	T Helper Type 22
TID	Three Times a Day
TLR	Toll-like Receptor
TNF	Tumor-Necrosis Factor
UGT	Uridine Glucoronyltransferase
ULN	Upper Limit of Normal
UV	Ultraviolet
UVB	Ultraviolet B
WBC	White Blood Cells
WOCBP	Women of Child Bearing Potential

Trademark Information

Trademarks of the GlaxoSmithKline group of companies
DiffCORE
RAMOS NG

Trademarks not owned by the GlaxoSmithKline group of companies
Otezla
QuantiFERON-TB Gold PLUS

10.9. Appendix 9: Protocol Amendment History

The Protocol Amendment Summary of Changes Table for the current amendment is located directly before the Table of Contents (TOC).

Amendment [02]: (14-JUL-2020)

Overall Rationale for the Amendment: To include additional safety monitoring for participants in the study in response to the COVID-19 pandemic.

Section # and Name	Description of Change	Brief Rationale
Section 1.1 Study Synopsis Section 9.2 Sample Size Determination	Revised the allowable number of replacement participants to be randomised (from up to approximately 3 to up to approximately 6) to ensure that approximately 21 have completed the Week 4 visit.	Amended due to anticipated impact of COVID pandemic on participant retention
Section 1.3 Schedule of Activities	Updated to add COVID-19 testing and monitoring of COVID-19 signs and symptoms.	Additional safety monitoring
Section 5.2 Exclusion Criteria	Added exclusion criteria to exclude study participants who have a positive test for SARS-CoV-2 at screening or interaction with known COVID-19 positive contacts within 14 days prior to Day 1. In addition, expanded exclusion criteria to exclude study participants that may have any other considerations (not just medical	Additional safety monitoring
	conditions) that, in the opinion of the Investigator, would put the participant at unacceptable risk.	

Section # and Name	Description of Change	Brief Rationale
Section 7.2 Participation Discontinuation/Withdrawal from the Study	Added new information to include that a participant may be withdrawn from the study at any time if deemed to be demonstrating suspected, probable or confirmed COVID-19 infection.	Additional safety monitoring
Section 8.2.1 Physical Examination	Added text to remind Investigators to pay special attention to clinical signs related to previous serious illnesses or that could be related to infection (e.g. COVID-19).	Additional safety monitoring
Section 8.2.5 Suicidal Ideation and Behavior Risk Monitoring	Correction to clarify that the 'Baseline/Screening' version of the C-SSRS questionnaire is used at the Screening visit, and the 'Since Last Visit' version of the C-SSRS questionnaire is used at the Week 0/Day 1 visit.	Correction
Section 10.2 Clinical Laboratory Tests	COVID-19 (SARS-CoV-2) test added to list of Other Screening Tests.	Additional safety monitoring
Section 10.7 Appendix 7	Added to provide information on the measures to be taken to protect participants' safety, welfare and rights, and promote data integrity.	To outline measures that may be applicable for any site impacted by the COVID-19 pandemic.
Section 10.8 Abbreviations and Trademarks	Updated accordingly with new terminology.	Administrative Update

Amendment [01]: (09-APR-2020)

Overall Rationale for the Amendment: To address a request from Health Canada for clarification of contraception requirements and the QTc formula to be used in the study. In addition, some administrative corrections have been made to the protocol.

Section # and Name	Description of Change	Brief Rationale
Section 1.1 Synopsis	Brand name for apremilast added.	Clarification
	Grammatical corrections made.	Correction
	Wording updated to indicate that the interim futility analysis will be conducted when at least six participants receiving GSK2982772 have completed the Week 12 visit or discontinued study treatment.	Clarification
Section 1.3 Schedule of Activities (SoA)	Footnotes updated to indicate that Day 85 is a non-dosing day.	Clarification
	Text added to describe the circumstances in which biopsies would not be required at the Early Withdrawal visit.	Clarification
	Text added to indicate that Fridericia's formula (QTcF) must be used for QTc correction.	Restricted protocol to use of Fridericia's formula only in response to Health Canada feedback.

Section # and Name	Description of Change	Brief Rationale
Section 4.1 Overall Design	Correction to duration of treatment period.	Correction
	Wording updated to indicate that the interim futility analysis will be conducted when at least six participants receiving GSK2982772 have completed the Week 12 visit or discontinued study treatment.	Clarification
Section 5.1 Inclusion Criteria	The Female Participants Decision Tree has been removed from inclusion criterion 7 and replaced with text to improve clarity for the justification of contraceptive use in this study.	Clarification
Section 5.2 Exclusion Criteria	The option to use Bazett's formula for QTc has been removed.	In response to Health Canada
Section 7.1.2		feedback, restricted
QTc Stopping Criteria		protocol to use of Fridericia's formula only.
Section 2.2 Background	Minor typographical errors have been corrected.	Corrections
Section 2.3 Benefit/Risk Assessment		
Section 3 Objectives and Endpoints		
Section 4.3 Justification of Dose		
Section 5.3.1 Meal and Dietary Restrictions		
Section 6.3 Study Intervention Compliance		
Section 8.8 Biomarkers		

Section # and Name	Description of Change	Brief Rationale
Section 6.2 Measures to Minimise Bias: Randomisation and Blinding	Addition of text to make clear that randomisation will be stratified by prior biologic use.	Clarification
Section 8.2.1 Physical Examinations	Addition of text to indicate that height is measured at screening only.	Clarification
Section 8.2.3 Electrocardiograms	Approximate time to complete triplicate ECG readings has been updated.	To align with information in Section 7.1.2
Section 9.3 Population for Analysis	Addition of the definition of randomised population and clarification of other populations.	Clarification
Section 9.5 Interim Analyses	Wording updated to indicate that the interim futility analysis will be conducted when at least six participants receiving GSK2982772 have completed the Week 12 visit or discontinued study treatment.	Clarification
Section 10.1.7 Data Quality Assurance	Language added to indicate that quality tolerance limits have been pre-defined for the study.	Confirmation that Quality Tolerance Limits have been defined, to comply with ICH E6 R2 guidelines.
Section 10.2 Clinical Laboratory Tests	Pregnancy testing language has been updated to align with the Schedule of Activities (SoA).	Clarification
Section 10.7 Abbrevations and Trademarks	Otezla has been added to Trademark Information table.	Clarification

5.2. Primary Endpoint(s) Analyses.....	15
5.2.1. Definition of endpoint(s).....	15
5.2.2. Main analytical approach	15
5.2.3. Sensitivity analyses	17
5.2.4. Supplementary analyses.....	17
5.2.5. Subgroup analyses	17
5.3. Secondary Endpoint(s) Analyses	17
5.3.1. Definition of endpoint(s).....	17
5.3.2. Main analytical approach	18
5.3.3. Sensitivity analyses	21
5.3.4. Supplementary analyses.....	21
5.3.5. Subgroup analyses	21
5.4. Safety Analyses	21
5.4.1. Extent of Exposure	21
5.4.2. Adverse Events.....	21
5.4.2.1. Adverse Events of Special Interest.....	22
5.4.3. Laboratory Data.....	23
5.4.4. Vitals Signs.....	23
5.4.5. ECG.....	23
5.4.6. C-SSRS	24
5.5. Pharmacokinetic	24
5.5.1. Pharmacokinetic/Pharmacodynamic	25
5.6. Exploratory Endpoint(s) Analyses	25
5.6.1. Pharmacodynamic	25
5.7. Other Analyses	27
5.8. Interim Analyses	27
6. SUPPORTING DOCUMENTATION	28
6.1. Appendix 1 Abbreviations and Trademarks.....	28

6.1.1. List of Abbreviations	28
6.1.2. Trademarks	29
7. REFERENCES.....	30

Version history

This Statistical Analysis Plan (SAP) for study 208022 is based on the protocol dated 06-JAN-2021.

Table 1 SAP Version History Summary

SAP Version	Approval Date	Protocol Version (Date) on which SAP is Based	Change	Rationale
1	27MAR2020	1 (07JAN2020)	Not Applicable	Original version
2		3 (06JAN2021)	Clarification that statistical analyses will use a Bayesian approach and expected covariates updated.	Increased consistency in results being reported from the trial, given the primary analysis is using a Bayesian approach. Updated model text to include all expected covariates.
			Sensitivity analysis for binary missing data updated.	Since the time of writing, the impact of COVID-19, and therefore the chance of dropouts unrelated to trial activities, has increased. To assess this, the team have decided to include imputing missing PASI response with the response at the previous timepoint (LOCF approach) as a sensitivity to NRI.
			Clarification of endpoint and hypothesis text	Updated text to match current protocol wording.
			Addition of COVID and	COVID population added to reflect internal

SAP Version	Approval Date	Protocol Version (Date) on which SAP is Based	Change	Rationale
			Modified ITT analysis populations	standards for reporting COVID data. Modified ITT included to assess efficacy on participants who have completed Week 4 assessment (first timepoint of interest) as a supplementary population for efficacy assessments.
			Placebo prior	Clarification on the prior distribution to be used in primary analysis.
			Revision of planned analyses of skin biopsy data for PK and target engagement	Skin biopsy to be collected for PK and target engagement assays is no longer required under Protocol Amendment 3. The planned MMRM analysis of skin target engagement is not required but may be conducted if sufficient data available.

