9.4.1. Primary Analyses

Efficacy analyses will be based on the ITT population unless stated otherwise in the SAP. The primary analysis will assess the difference in PASI75 response rates between GSK2982772 960 mg and placebo at Week 12. A Bayesian logistic regression analysis of the difference in PASI75 response rates at Week 12 will be conducted to calculate posterior probabilities that the true effect of GSK2982772 relative to placebo is greater than a range values of interest.

An informative prior will be used for the placebo arm to leverage relevant historical placebo data into the analysis. It is expected that this prior will be a Beta (3.5, 46.5)

distribution, giving the historical data an effective sample size of 50 participants. Further emerging placebo data may be incorporated into the prior distribution for the placebo arm prior to breaking the study blind. A non-informative prior will be used for the PASI75 response rate on GSK2982772.

Participants who discontinue early or have missing PASI data at any visit will be treated as PASI75 non-responders at that time point (regardless of their response at previous visits). Sensitivity analyses will be conducted to investigate the impact of this approach to handling missing data.

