10.7. Appendix 7: COVID-19 Appendix

COVID-19 pandemic may impact the conduct of clinical studies. Challenges may arise from quarantines, site closures, travel limitations, interruptions to the supply chain for the investigational product or other considerations if site personnel or study participants become infected with COVID-19. These challenges may lead to difficulties in meeting protocol-specified procedures, including administering or using the investigational product or adhering to protocol-mandated visits and laboratory/diagnostic testing.

This protocol appendix outlines measures that may be applicable for any site impacted by the COVID-19 pandemic. The purpose of the appendix is to provide information on the measures to be taken to protect participants' safety, welfare and rights, and promote data integrity.

These measures will remain in place until until study completion.

STUDY PROCUDURES DURING COVID-19 PANDEMIC

During the special circumstances caused by the COVID-19 pandemic, you should consider specific public health guidance, the impact of any travel restrictions implemented by local/regional health authorities and local institutions, and individual benefit /risk when making enrollment and treatment decisions for trial participants. Guidance on how to deal with participants who develop COVID-19 symptoms during the study are described in the SRM.

As outlined in Section 8, protocol waivers or exemptions are not allowed and every effort should be made to adhere to protocol-specified assessments for participants on study intervention, including follow up. However, when not possible, for the duration of these special circumstances, the following measures may be implemented for enrolled participants.

• Clinical investigators should document in site files and in participant notes as appropriate how restrictions related to COVID-19 led to the changes in study conduct and duration of those changes and indicate which trial participants were impacted and how those trial participants were impacted (as per the current local COVID-19 related regulatory guidance).

Missing protocol required data/visits due to COVID-19 should be noted in participant notes, captured in the eCRF and recorded as a COVID-19 protocol deviation.

Protocol Defined Procedures/Visits:

• The protocol defined interval for the collection of samples during the follow-up visit (see Section 1.3 Schedule of Activities), may be extended up to a maximum length of 14 days.

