5.2.2. Main analytical approach

The primary analysis will be produced for the ITT population.

The summary measure of interest is the difference in PASI75 response rates at Week 12 (Day 85) between GSK2982772 and placebo. Missing values will be imputed as non-responders.

The primary endpoint will be analysed using a Bayesian logistic regression model, details given in [Table 2](#). Summary statistics will be provided for the posterior distribution of the true difference in PASI75 response rate (GSK2982772 vs placebo) as well as posterior probabilities for a range of thresholds.

A non-informative prior will be used for the PASI75 response rate on GSK2982772 and covariates.

An informative prior will be used for the placebo response rate of the form: 90% weight on $Be(5.39, 69)$ and 10% on $Be(1/3, 1/3)$. The prior was derived from historical data from similar clinical trials using meta-analytic predictive prior (MAP) approach, the effective sample size is approximately 63 [[Schmidli, 2014](#)].

In the event that the placebo prior is different from what is presented here, this will be documented in the CSR.

Table 2 Statistical Analysis of Primary Endpoint

Endpoint(s)	

 PASI75 response at Week 12 (Day 85) 	
Analysis Method	
Bayesian Logistic Regression (using informative prior)	
Model Specification	
Outcome	$y_i = \text{Response (0/1) for participant } i$
Predictors	
 Treatment (categorical) Prior Biologic Use (categorical) Baseline PASI score (continuous) 
Unless stated otherwise the predictors (not including study treatment) will be centered around their estimated mean prior to inclusion in the model

Model	$y_i \sim \text{Ber}(p_i)$ $\text{logit}(p_i) = (\text{Treatment=Placebo}) \times \beta_1 + (\text{Treatment=GSK}) \times \beta_2 + (\text{Prior Biologic Use}^*) \times \beta_4 + (\text{Baseline PASI score}^*) \times \beta_5$
Prior distributions for coefficients (β)	β = fixed effect parameters associated to predictors 
 β_1: informative prior such that $\text{logit}^{-1}(\beta_1) \sim$ mixture of Betas* β_2: non-informative prior such that $\text{logit}^{-1}(\beta_2) \sim \text{Beta}(1/3, 1/3)$ Other β_k: non-informative priors of $N(0, SD=100)$ 
*Expected prior is a mixture of $Be(5.39, 69)$ and $Be(1/3, 1/3)$, weighted to 90% and 10% respectively. Final prior will be reported in the CSR.

Model Checking & Diagnostics	
See Section 5.1.1	

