5.2.3. Sensitivity analyses

Where informative priors have been used, a sensitivity analysis using vague priors (no historical borrowing) will also be produced.

Additional sensitivity analyses to assess the impact the missing data handling for binary data may be produced, such as using a LOCF approach to missing data.

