5.2.4. Supplementary analyses

A supplementary analysis where the primary analysis is repeated using the Modified ITT population may be produced to assess the treatment effect in subjects able to complete at least 4 weeks of treatment. A frequency table of PASI response using this population would also be produced.

Off-treatment PASI data, collected following treatment discontinuation prior to Week 12, may be used for additional supplementary analyses if available.

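### No pre-specified efficacy analysis uses the recorded COVID-19 reason for missing data, so none separates COVID-19 losses from treatment-related ones

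*SAP*

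**What the plan says.** SAP Table 1 (version history) gives the reason for updating the binary missing-data sensitivity analysis: "Since the time of writing, the impact of COVID-19, and therefore the chance of dropouts unrelated to trial activities, has increased". It names LOCF as the way to assess this.

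Protocol Appendix 7 says how such gaps are recorded: "Missing protocol required data/visits due to COVID-19 should be noted in participant notes, captured in the eCRF and recorded as a COVID-19 protocol deviation". Protocol 7.2 separately allows withdrawal for suspected, probable or confirmed COVID-19.

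The rules for the primary endpoint are:

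- Protocol 9.4.1: "Participants who discontinue early or have missing PASI data at any visit will be treated as PASI75 non-responders at that time point".
- SAP 5.2.2: "Missing values will be imputed as non-responders".
- SAP 5.2.3, for missing-data sensitivity: "sensitivity analyses to assess the impact the missing data handling for binary data may be produced, such as using a LOCF approach".
- SAP 5.2.4: "A supplementary analysis where the primary analysis is repeated using the Modified ITT population may be produced". SAP section 4 defines that set by completion of the Week 4 assessment.

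The COVID-19 analysis set (SAP section 4) is defined by a case diagnosis. SAP 5.1 uses it for COVID outputs and a subset of safety analyses.

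**The concern.** The stated question is how far drop-outs unrelated to the trial affect the result. The planned tools cannot answer it, because none of them looks at the reason. Under the primary rule, a participant who misses Week 12 because of quarantine counts as a failure, exactly like one who stopped for an adverse event or lack of effect. LOCF, if it is run, re-scores both kinds. A shift between the two analyses therefore cannot be attributed to COVID-19, whichever imputation is used.

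With 14 active participants, one or two such losses are a material share of the arm. If the observed difference falls short of the SAP's 45-point threshold, no planned analysis shows whether the drug fell short or participants were lost for reasons unrelated to it.

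**Working it through.** **Inputs.** 14 active and 7 placebo (SAP Table 2, interim analysis). Placebo rate 7% and difference 55 points, hence 62% on active (protocol 9.2, SAP section 3). Active prior Beta(1/3, 1/3). Placebo prior 0.9·Beta(5.39, 69) + 0.1·Beta(1/3, 1/3) (SAP 5.2.2). The two criteria are those listed for the interim predictive probabilities in SAP Table 2:

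- zero criterion: posterior probability above 97.5% that the difference exceeds 0;
- 45-point criterion: posterior probability above 55% that the difference exceeds 45 points.

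The documents give no COVID-19 loss rate, so the loss counts below are assumptions. Covariates and replacements are left out.

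**Method.** With a responders of n on active, the posterior is Beta(1/3 + a, 1/3 + n − a). With p responders of m on placebo, each mixture component becomes Beta(α + p, β + m − p), and its weight is multiplied by B(α + p, β + m − p)/B(α, β) and renormalised. The chance of meeting a criterion is the sum, over all (a, p) that meet it, of Bin(a; observed active, 0.62) × Bin(p; observed placebo, 0.07). Failure scoring keeps n = 14 and m = 7. Treating losses as missing uses the observed denominators. Without covariates, this is what drawing the missing values inside the model amounts to.

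**The plan's own figure.** With the Beta(3.5, 46.5) placebo prior, the zero criterion is met with probability 0.997, against the stated approximately 99%. With the SAP mixture prior it is 0.981. The set-up reproduces the plan.

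**Results with the SAP mixture prior.**

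| COVID-19 losses | 45-point, as failures | 45-point, as missing | Zero, as failures | Zero, as missing |
|---|---|---|---|---|
| None | 0.741 | 0.741 | 0.981 | 0.981 |
| 1 active | 0.628 | 0.740 | 0.973 | 0.982 |
| 2 active | 0.492 | 0.714 | 0.961 | 0.973 |
| 3 active + 1 placebo | 0.344 | 0.720 | 0.952 | 0.974 |

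**Where it turns.** With no placebo responders among 7, the 45-point criterion needs 8 of 14 active responders: 8/14 gives a posterior probability of 0.66, and 7/14 gives 0.46. Now take 2 active losses and 1 placebo loss, with no placebo responders observed. The posterior probability that the difference exceeds 45 points is:

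| Active responders among 12 observed | As failures (of 14 and 7) | As missing (of 12 and 6) |
|---|---|---|
| 6 | 0.26 | 0.46 |
| 7 | 0.46 | 0.68 |
| 8 | 0.66 | 0.85 |

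Only 7 responders changes the outcome. Its probability at a 62% rate is C(12,7) × 0.62⁷ × 0.38⁵ ≈ 0.22. At that count, the posterior probability of a difference above zero is at least 0.999 under either method.

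**The case against.** A reader might infer that the trial cannot tell COVID-19 losses from other losses. The documents do not support that. The reason is captured in the eCRF and logged as a protocol deviation, important deviations are summarised (SAP 4.1), and a post hoc split of 21 participants is simple. What is missing is pre-specification. That matters because SAP 5.1 to 5.3 set the analyses in advance, and a split chosen after seeing the data carries less weight.

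A reader might also treat Table 1 and SAP 5.2.3 as contradicting each other, since one says LOCF was added and the other leaves it optional. Table 1 is a change log, so no error is claimed on that ground. It is used here only for the purpose it states. SAP 5.2.3 states a broader aim, the effect of missing-data handling in general, and LOCF against the primary rule does serve that aim.

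Other measures soften the point:

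- Up to about 6 replacements are allowed. However, the ITT set keeps every randomised and dosed participant, so a dosed participant who was replaced still counts as a failure.
- Modified ITT removes losses before Week 4 and is used for the interim PASI75 analysis, but it selects on completion and not on reason.
- Change in PASI score is modelled under missing at random (SAP 5.3.2), so losses are not failures there.
- Off-treatment PASI may be used if available (SAP 5.2.4).

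None of these separates reasons for PASI75.

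Three limits stand. The zero criterion, on which the sample size rests, hardly moves. The 45-point rule is one of several interim decision criteria, and SAP section 2 sets an estimation objective with no success threshold. The OPS, which holds data-handling conventions, was not available, although SAP 1.2.2 places the missing-data rules in the SAP's own analysis sections.

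**Conclusion.** The point holds as a gap in pre-specification. The protocol and SAP record the COVID-19 reason for missing data and visits and name unrelated drop-outs as something to assess, but contain no efficacy analysis that uses the reason.

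The cost falls on the 45-point criterion. Failure scoring of the assumed losses takes 11, 22 and 38 percentage points off the chance of meeting it (0.740 − 0.628, 0.714 − 0.492, 0.720 − 0.344), compared with treating the same losses as missing. On the zero criterion the gap is about 1 to 2 points. These sizes rest on the plan's 62% versus 7%, the SAP mixture prior, no covariates, no replacements, and COVID-19 losses unrelated to response.

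Nothing here shows that non-responder imputation is the wrong primary rule, or that the trial's conclusion would usually reverse. In the worked example, only one responder count does so.

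**What to change.** Keep non-responder imputation as the primary rule. In SAP 5.2.3, commit to one further analysis. Week 12 PASI75 is treated as missing, and drawn within the Table 2 model, only where COVID-19 is shown as the cause by the eCRF missing-visit record or, for a withdrawal, by the recorded disposition reason. All other missing values stay non-responders. The disposition reason is needed because Appendix 7 shows the eCRF record for missing data and visits only. The sponsor should confirm that COVID-19 withdrawals can be identified that way.

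Beside the primary result, tabulate missing Week 12 PASI by arm and reason. That table alone gives much of the benefit.

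The cost is SAP wording, one table and one extra model run, with no new visits or design change. The downside is an untestable assumption that COVID-19-related missingness is unrelated to response, which is why this stays a sensitivity analysis.
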